10.1 VISIT SCHEDULE

10.1.1 Run-in period

Following the screening for inclusion / exclusion criteria as noted in [Section 7](#), patients not at stable doses of atorvastatin or other statins, unstable non-statin LMTs, or unstable diet therapy alone are enrolled (Week -7 / Visit 1). Stabilization of daily 5mg atorvastatin dosing, non-statin LMTs, or diet therapy will be carried out as necessary.

- On site visit
- Complete informed consent – the patients will receive complete information about the study both verbally and in writing. Written informed consent for the study must be obtained prior to any study related investigations.

Note: All AEs and SAEs will be collected from the time of informed consent signature and throughout the study until Week 64 (Visit 23).

- Obtain patient demography – age, gender, and race.
- Assess inclusion / exclusion criteria
- Obtain medical history (including menopausal status), surgical history, alcohol habits, and smoking habits.
- Obtain family medical history (including risk factors relating to premature CHD [before 55 years of age in a male and 65 years in a female first degree relative], allergy and type-2 diabetes).
- Document prior medication history within the previous 8 weeks, especially for lipid modifying therapies (including statin) and nutraceutical products that may affect lipids (e.g., omega-3 fatty acids, plant stanols such as found in Benecol, flax seed oil, psyllium).
- Perform physical examination

- Contact IVRS/IWRS for notification of entering the run-in period. Patient number will be allocated by the IVRS / IWRS. This patient number is composed of a 9-digit number containing the 3-digit country code, the 3-digit center code and the 3-digit patient chronological number (3-digit patient chronological number is 001 for the first patient screened in a center, 002 for the second patient screened in the same center).
- Review patient's diet. Patient should be on a diet following Japan Atherosclerosis Society Guideline or equivalent (see [Section 17](#), Appendix B).
- Record concomitant medication.
- Measure vital signs including HR and BP.
- Collect AEs/SAEs information from this point onward.
- An appointment will be given for the next visit.
- Provide instruction on diet.

10.1.2 Screening period

Only patients with stable 5 mg daily atorvastatin, non-statin LMTs, or diet therapy alone, who meet the inclusion criteria as noted in [Section 7.1](#) should be screened. The screening period will take place up to 3 weeks or 21 days (and as short as possible, upon receipt of laboratory eligibility criteria) prior to randomization / Day 1 visit (Week 0). The first screening visit (Week -3) can take place from 8 to 21 days before the randomization visit. If it is planned to have another designated person administer the injections to the patient during the study, then this person should be present at the injection training visit (Week -1).

Screening Visit (Visit 2 / Week -3 / Day -21 up to Day -8):

- On-site visit.

Complete informed consent if the patients skip the run-in period and directly enter the screening period. The patients will receive complete information about the study both verbally and in writing. Written informed consent for the study must be obtained prior to any study related investigations.
- Obtain patient demography - age, gender, and race of the patient can skip the run-in period.
- Assess inclusion / exclusion criteria.
- Obtain medical history (including menopausal status), surgical history, alcohol habits, and smoking habits.
- Obtain family medical history (including risk factors relating to premature CHD [before 55 years of age in a male and 65 years in a female first degree relative], allergy and type-2 diabetes).

- Document prior medication history within the previous 12 weeks, especially for lipid modifying therapy (including statin) and nutraceutical products that may affect lipids (e.g., omega-3 fatty acids, plant stanols such as found in Benecol, flax seed oil, psyllium).
- Perform physical examination
- Measurement of body weight and body height.
- Contact IVRS/IWRS for notification of screening. Patient number will be allocated by the IVRS/IWRS. This patient number is composed of a 9-digit number containing the 3-digit country code, the 3-digit center code and the 3-digit patient chronological number (3-digit patient chronological number is 001 for the first patient screened in a center, 002 for the second patient screened in the same center).

Review patient's diet. Patient should be on a diet following Japan Atherosclerosis Society Guideline or equivalent (see [Section 17](#), Appendix B).

- Record concomitant medication.
- Collect AEs/SAEs information.
- Measure vital signs including HR and BP.
- Perform 12-lead ECG recording
- Obtain fasting blood sample for:
 - Lipids: total-C, measured and/or calculated LDL-C, HDL-C, TG, non-HDL-C.
 - Hematology: CBC including hematocrit, RDW, reticulocyte count, hemoglobin, red blood cell count, white blood cell count with differential count and platelets.
 - Chemistry: glucose, sodium, potassium, chloride, bicarbonate, calcium, phosphorous, urea nitrogen, creatinine, eGFR, uric acid, LDH, total protein, albumin, haptoglobin and γ -GT.
 - CPK.
 - Liver panel (ALT, AST, ALP, and total bilirubin).
 - Hepatitis B surface antigen and hepatitis C antibody tests.
 - Serum pregnancy test (women of childbearing potential only).
 - HbA_{1c}.
 - TSH.
- Urinalysis (dipstick including pH, specific gravity, the presence of blood, protein, glucose, ketones, nitrites, leukocyte esterase, urobilinogen, and bilirubin, and microscopic examination).

Note: All patients will be qualified for randomization based on the laboratory results LDL-C value obtained at this visit.

- An appointment will be given for the next visit (Week -1).

- Provide instruction on diet.
- If it is planned to have another designated person administer the injections to the patient during the study, then the person also should be present at the next visit (injection training visit at Week -1).

Injection training visit at Screening (Visit 3 / Week -1 / Day -7 ± 6):

Note: Injection training will be carried out if patient prefers self-IMP injection.

- On-site visit
- IVRS/IWRS contact for allocation of a batch number for training kit.
- Record batch number allocated in e-CRF.
- Injection training should be provided as outlined in [Section 8.1](#). The placebo for alirocumab should be administered by the patient or another designated person (such as spouse, relatives, etc.) at the study site under direct supervision of site staff with appropriate feedback.
- Measure vital signs including HR and BP.
- Collect AEs / SAEs information.
- If patient will undergo the second optional injection training with alirocumab placebo, then the following steps are required. However, if patient does not need a second optional training injection with alirocumab placebo then do not perform these steps:
 - Re-contact IVRS / IWRS for allocation of a second new batch number for a second training kit.
 - Record and dispense the second batch number allocated in e-CRF.
 - Dispense the second placebo training injection to the patient for self-administration.

Note: Further training with the scheduled double-blind / open-label IMP can be done at any time during the study as necessary. The required process for the training is described above.

- An appointment will be given for the next visit (Week -1 or 0).
- Remind patient to be in fasting conditions (i.e., overnight, at least 10 to 12 hours fast and refrain from smoking) for next visit. Also alcohol consumption within 48 hours and intense physical exercise within 24 hours preceding the next visit are discouraged.

10.1.3 Double-blind treatment period (Study Site Visits)

10.1.3.1 Randomization visit (Visit 4 / Week 0 /Day 1)

Note: Blood sample should be collected before IMP administration.

- On-site visit
- Assess Inclusion / Exclusion Criteria.

- Perform physical examination.
- Measure body weight.
- If the patient is confirmed eligible (and in fasting conditions), the Investigator will start the next study procedures:
 - IVRS/IWRS contact for randomization and allocation of a 7-digit treatment kit number according to the randomization list for the alirocumab injection. Investigator should never allocate a treatment kit number to a patient without contacting IVRS/IWRS.
 - Double-blind IMP kits dispensation as per treatment kit numbers provided by IVRS/IWRS along with schedule reminder. The patient injection instruction manual and treatment administration package should be provided.
 - The first double-blind IMP injection will take place at the study site, but only after the collection of the fasting blood samples and after the assessment of all evaluations planned at that visit.
 - The patients should be observed for at least 30 minutes after the IMP injection.
 - In case of self-IMP injection, close supervision, feedback and further training to be provided for IMP administration when necessary.
- Review patient's diet. Patient should be on a diet recommended by the Japan Atherosclerosis Society Guideline or equivalent.
- Record concomitant medication.
- Measure vital signs including HR and BP.
- Collect AEs / SAEs information.
- Obtain fasting blood sample for:
 - Lipids: total-C, measured and/or calculated LDL-C, HDL-C, TG, non-HDL-C, Apo-B, Apo A-1, Apo-B / Apo A-1 ratio, and Lp(a).
 - Hematology: CBC including hematocrit, RDW, reticulocyte count, hemoglobin, red blood cell count, white blood cell count with differential count and platelets.
 - Chemistry: glucose, sodium, potassium, chloride, bicarbonate, calcium, phosphorous, urea nitrogen, creatinine, eGFR, uric acid, LDH, total protein, albumin, haptoglobin and γ -GT.
 - CPK.
 - Liver panel (ALT, AST, ALP, and total bilirubin).
- Urinalysis (dipstick and microscopy).
- Urine pregnancy test (WOCBP).
- Anti-alirocumab antibodies.
- Serum alirocumab concentration (PK).
- [REDACTED]

- [REDACTED]
- [REDACTED]
- Reminders:
 - An appointment will be given for the next study site visit (Week2).

Note: If patients (and/or their designated persons [such as a spouse, relative, etc.]), who prefer self-IMP administration and their self-IMP injection capabilities are accepted by the site Investigators based on the Injection training session(s) during the Screening visit (Week -1), patients will administer the IMP by themselves during the course of study. The self-IMP administration will be carried out during the DBTP under direct supervision of Investigators and the site staff so that both of patient and the site Investigator can confirm the self-IMP administration capability of the patient before the OLTP will start.

10.1.3.2 Visit 5 / Week 2 (Day 15 ± 7)

Note: No blood sampling is scheduled.

- On-site visit
- IVRS/IWRS contact for allocation of a treatment kit according to the randomization list.
- IMP administration and compliance check, and 30 minutes observation after the IMP administration.
- Record concomitant medication.
- Measure vital signs including HR and BP.
- Collect AEs/SAEs information.
- Reminders:
 - An appointment will be given for the next study site visit (Week 4).
 - Remind patient to be in fasting conditions (i.e., overnight, at least 10 to 12 hours fast and refrain from smoking) for next study site visit. Also alcohol consumption within 48 hours and intense physical exercise within 24 hours preceding the next study site visit are discouraged.

10.1.3.3 Visit 6 / Week 4 (Day 29 ± 7)

Note: Blood sample should be collected before IMP administration.

- On-site visit
- IVRS/IWRS contact for allocation of a treatment kit according to the randomization list.
- IMP administration and compliance check, and 30 minutes observation after the IMP administration.

- Record concomitant medication.
- Measure vital signs including HR and BP.
- Collect AEs / SAEs information.
- Obtain fasting blood sample for:
 - Lipids: total-C, measured and/or calculated LDL-C, HDL-C, TG, and non-HDL-C.
 - Liver panel (ALT, AST, ALP, and total bilirubin).
- Anti-alirocumab antibodies.
- Serum alirocumab concentration (PK).
- Reminders:
 - An appointment will be given for the next study site visit (Week 6).

10.1.3.4 Visit 7 / Week 6 (Day 43 ± 7)

Note: No blood sampling is scheduled.

- On-site visit
- IVRS/IWRS contact for allocation of a treatment kit according to the randomization list.
- IMP administration and compliance check, and 30 minutes observation after the IMP administration.
- Record concomitant medication.
- Measure vital signs including HR and BP.
- Collect AEs / SAEs information.
- Reminders:
 - An appointment will be given for the next study site visit (Week 8).
 - Remind patient to be fasting conditions (i.e., overnight, at least 10 to 12 hours fast and refrain from smoking) for next study site visit. Also alcohol consumption within 48 hours and intense physical exercise within 24 hours preceding the next study site visit are discouraged.

10.1.3.5 Visits 8 / Week 8 (Day 57 ± 7)

Note: Blood sample should be collected before IMP administration.

- On-site visit
- IVRS/IWRS contact for allocation of a treatment kit according to the randomization list.
- IMP administration and compliance check, and 30 minutes observation after the IMP administration.

- Record concomitant medication.
- Measure vital signs including HR and BP.
- Collect AEs / SAEs information.
- Obtain fasting blood sample for:
 - Lipids: total-C, measured and/or calculated LDL-C, HDL-C, TG, non-HDL-C, Apo-B, Apo A-1, Apo-B / Apo A-1ratio, and Lp(a).
 - Liver panel (ALT, AST, ALP, and total bilirubin).
- Serum alirocumab concentration (PK).
- Reminders:
 - An appointment will be given for the next study site visit (Week 10).
 - Remind patient to be fasting conditions (i.e., overnight, at least 10 to 12 hours fast and refrain from smoking) for next study site visit. Also alcohol consumption within 48 hours and intense physical exercise within 24 hours preceding the next study site visit are discouraged.

10.1.3.6 Visit 9 / Week 10 (Day 71 ± 3)

Note: Blood sample should be collected before IMP administration.

- On-site visit.
- IVRS/IWRS contact for allocation of a treatment kit according to the randomization list.
- IMP administration and compliance check, and 30 minutes observation after the IMP administration.
- Record concomitant medication.
- Measure vital signs including HR and BP.
- Collect AEs / SAEs information.
- Obtain fasting blood sample for:
 - Lipids: total-C, measured and/or calculated LDL-C, HDL-C, TG, non-HDL-C, Apo-B, Apo A-1, Apo-B / Apo A-1 ratio, and Lp(a).
- Serum alirocumab concentration (PK).
- Reminders:
 - An appointment will be given for the next study site visit.
 - Remind patient to be fasting conditions (i.e., overnight, at least 10 to 12 hours fast and refrain from smoking) for next study site visit. Also alcohol consumption within 48 hours and intense physical exercise within 24 hours preceding the next study site visit are discouraged.

10.1.3.7 Visit 10 / Week 12 (Day 85 ± 3): End of DBTP and Start of OLTP

Note: Blood sample should be collected before IMP administration.

- On-site visit.
- Perform physical examination.
- Measure body weight.
- IVRS / IWRS contact for allocation of a treatment kit according to the randomization list.
- Review patient's diet. Patient should be on a diet recommended by the Japan Atherosclerosis Society Guideline or equivalent.
- IMP administration and compliance check, and 30 minutes observation after the IMP administration.
- Record concomitant medication.
- Measure vital signs including HR and BP.
- Collect AEs/SAEs information.
- Record 12-lead ECG.
- Obtain fasting blood sample for:
 - Lipids: total-C, measured and/or calculated LDL-C, HDL-C, TG, non-HDL-C, Apo-B, Apo A-1, Apo-B / Apo A-1 ratio, and Lp(a).
 - Hematology: complete blood cell count (CBC) including hematocrit, red blood cell distribution width (RDW), reticulocyte count, hemoglobin, red blood cell count, white blood cell count with differential count and platelets. (Reticulocyte count and haptoglobin are measured only when hemoglobin is decrease with ≥ 1.5 g/dL from the baseline).
 - Chemistry: glucose, sodium, potassium, chloride, bicarbonate, calcium, phosphorous, urea nitrogen, creatinine, eGFR, uric acid, lactate dehydrogenase (LDH), total protein, albumin, haptoglobin and γ -GT.
 - CPK.
 - Liver panel (ALT, AST, ALP, and total bilirubin).
- Urinalysis (dipstick and microscopy).
- Urine pregnancy test (WOCBP).
- HbA_{1c}
- Anti-alirocumab antibodies.
- Serum alirocumab concentration (PK).
- [REDACTED]

10.1.4 Open-label treatment period (Study Site Visits or Phone Call Visits)

10.1.4.1 Visit 10 / Week 12 (Day 85 ± 3): End of DBTP and Start of OLTP

Note: The OLPT starts from this visit and it is also the last visit of the DBTP. Blood sample should be collected before the IMP administration. The patient who performs self-IMP administration during the DBTP will continue the self-IMP administration at his/her home during the OLTP. Site staff has to carefully monitor the IMP administration compliance and AEs and SAEs collection through phone-visit call.

- On-site visit.
- Perform physical examination.
- Measure body weight.
- IVRS / IWRS contact for allocation of a treatment kit and the IMP will be supplied before Week 24 scheduled visit.

Note: All patients will be treated with alirocumab 150 mg Q4W from this time point.

- IMP administration and compliance check, and 30 minutes observation after the IMP administration.
- Review patient's diet. Patient should be on a diet recommended by the Japan Atherosclerosis Society Guideline or equivalent.
- Record concomitant medication.
- Measure vital signs including HR and BP.
- Collect AEs / SAEs information.
- Record 12-lead ECG.
- Obtain fasting blood sample for:
 - Lipids: total-C, measured and/or calculated LDL-C, HDL-C, TG, non-HDL-C, Apo-B, Apo A-1, Apo-B / Apo A-1 ratio, and Lp(a).
 - Hematology: CBC including hematocrit, RDW, reticulocyte count, hemoglobin, red blood cell count, white blood cell count with differential count and platelets. (Reticulocyte count and haptoglobin are measured only when hemoglobin is decrease with $\geq 1.5\text{g/dL}$ from the baseline).
 - Chemistry: glucose, sodium, potassium, chloride, bicarbonate, calcium, phosphorous, urea nitrogen, creatinine, eGFR, uric acid, LDH, total protein, albumin, haptoglobin and γ -GT.
 - CPK.
 - Liver panel (ALT, AST, ALP, and total bilirubin).
- Urinalysis (dipstick and microscopy).
- Urine pregnancy test (WOCBP).

- HbA_{1c}
- Anti-alirocumab antibodies.
- Reminders:
 - An appointment will be given for the next study site visit (Week 16).

10.1.4.2 Visit 11 / Week 16 (Day 113 ± 7)

- Phone call visit (or IMP injection site visit).

Note: If the patient decides not to have self-IMP administration at his/her home, the patient can visit the site as the “IMP injection site visit” for IMP administration, and the site staff or the patient under direct site staff supervision can administer the IMP.

- IMP administration and compliance check, and 30 minutes observation after the IMP administration.
- Record concomitant medication.
- Collect AEs / SAEs information.
- Reminders:
 - An appointment will be given for the next study site visit (Week 20).
 - Remind patient to be fasting conditions (i.e., overnight, at least 10 to 12 hours fast and refrain from smoking) for the Week 20 scheduled study site visit. Also alcohol consumption within 48 hours and intense physical exercise within 24 hours preceding the next study site visit are discouraged.

10.1.4.3 Visit 12 / Week 20 (Day 141 ± 7)

Note: Blood sample should be collected before IMP administration.

- On-site visit.
- IMP administration and compliance check, and 30 minutes observation after the IMP administration.
- Record concomitant medication.
- Measure vital signs including HR and BP.
- Collect AEs/SAEs collection.
- Obtain fasting blood sample for:
 - Lipids: total-C, measured and/or calculated LDL-C, HDL-C, TG, and non-HDL-C.
- Reminders:
 - An appointment will be given for the next study site visit (Week 24).
 - Remind patient to be fasting conditions (i.e., overnight, at least 10 to 12 hours fast and refrain from smoking) for the Week 24 scheduled study site visit. Also alcohol

consumption within 48 hours and intense physical exercise within 24 hours preceding the next study site visit are discouraged.

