11 STATISTICAL CONSIDERATIONS

11.1 DETERMINATION OF SAMPLE SIZE

The study is expected to enroll approximately 159 patients.

Two pairwise comparisons will be performed (alirocumab 150 mg Q4W versus placebo and alirocumab 150 mg Q2W vs. placebo). In order to handle multiple comparisons Bonferroni adjustment will be used, i.e., the alpha level for each comparison is 0.025 to obtain an overall study alpha level of 0.05.

A sample size of 38 patients in the ITT population (19 in alirocumab group and 19 in placebo group) will have 90% power to detect a difference of 30% in mean percentage change in calculated LDL-C in any pairwise comparison with a 0.025 two-sided significance level and assuming a common standard deviation of 25%.

As a result, the total sample size needed for efficacy will be 57 patients (19 in each of the two alirocumab arms and 19 in the placebo arm).

The sample size is also considered in order to obtain long-term safety data. A sample size of 159 patients (randomization ratio 1: 1: 1, i.e., 53 in alirocumab 150 mg Q4W, 53 in alirocumab 150 mg Q2W, and 53 in placebo) will allow having long-term open-label safety data. With this sample size, 100 patients are expected to be exposed to alirocumab for a minimum of 12 months providing that the proportion of drop out in the entire study duration (from randomization to Week 64) is 36%, which is obtained using exponential distribution with the same hazard as that of 30% dropout rate within 12 months. Moreover, with 100 patients treated with alirocumab for at least 12 months, AEs with a rate ≥ 0.03 will be detected with 95% probability.

Therefore, 159 patients (53 in alirocumab 150 mg Q4W, 53 in alirocumab 150 mg Q2W, and 53 in placebo) will be needed to evaluate both efficacy and safety.

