- The open-label RESIDUAL TREATMENT period: defined as the time from the day of last dose of open-label IMP injection +22 days up to the day of last dose of open-label IMP injection +70 days (10 weeks).
- The open-label POST-TREATMENT period: defined as the time starting the day after the end of the open-label TEAE period (i.e., 71 days after the day of last dose of open-label IMP injection).

Observation periods below will be analyzed at the first step analysis only.

- The alirocumab exposed TEAE period is defined as follows :
 - For alirocumab 150 mg Q4W group and alirocumab 150 mg Q2W group: The time from the first dose of double-blind IMP injection to the last dose of IMP injection (double-blind or open-label) + 70 days (10 weeks).

- For placebo Q2W group: The time from the first dose of open-label IMP injection to the last dose of open-label IMP injection + 70 days (10 weeks).

The alirocumab exposed TEAE period will include:

- The alirocumab exposed TREATMENT period: defined below:
 - For alirocumab 150 mg Q4W group and alirocumab 150 mg Q2W group: The time from the first dose of double-blind IMP injection to the last dose of IMP injection (double-blind or open-label) + 21 days.
 - For placebo Q2W group: The time from the first dose of open-label IMP injection to the last dose of open-label IMP injection + 21 days.
- The alirocumab exposed RESIDUAL TREATMENT period: defined below:
 - For alirocumab 150 mg Q4W group and alirocumab 150 mg Q2W group: The time from the day of last dose of IMP injection(double-blind or open-label) +22 days up to the day of last dose of IMP injection(double-blind or open-label) +70 days (10 weeks).
 - For placebo Q2W group: The time from the day of last dose of open-label IMP injection +22 days up to the day of last dose of open-label IMP injection +70 days (10 weeks).

The double-blind on-study observation period is defined as the time from the day of first dose of double-blind IMP injection until the last protocol planned double-blind visit of the patient. The last protocol planned double-blind visit is defined as the follow-up visit if done, or a maximum of 20 weeks after the randomization of the patient, for patients not proceeding into OLTP. For patients proceeding into OLTP, the last protocol planned double-blind visit is defined as the end of double-blind treatment period visit (Week 12).

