2.1.4.3 Laboratory safety variables

Clinical laboratory data consists of blood analysis, including hematology, clinical chemistry, and urinalysis. Clinical laboratory values after conversion will be analyzed into standard international units. International units will be used in all listings and tables. Clinical laboratory values converted into conventional (US) units will be also available in the database. Analyses can be provided upon request.

Unless otherwise specified below, blood samples for clinical laboratories were to be collected during:

- Screening period at Visit 2 (Week -3)
- DBTP at Visit 4 (Week 0), Visit 10 (Week 12) /or permanent treatment discontinuation
- OLTP at Visit 13 (Week 24), Visit 16 (Week 36), Visit 19 (Week 48), and Visit 23 (Week 64) /or permanent treatment discontinuation

- Follow-up period (Visit 24 [Week 72]) in case of abnormality at Visit 23 (Week 64).

The laboratory parameters (excluding those considered as efficacy parameters) will be classified as follows:

- Hematology:
 - Red blood cells and platelets:
red blood cell count, hemoglobin, red blood cell distribution width (RDW), reticulocyte count, hematocrit, platelets, haptoglobin;
 - White blood cells:
white blood cell count, neutrophils, lymphocytes, monocytes, basophils, eosinophils.
- Clinical chemistry:
 - Metabolism: glucose, total protein, albumin, creatine phosphokinase;
 - Electrolytes: sodium, potassium, chloride, bicarbonate, calcium, phosphorus;
 - Renal function: creatinine, glomerular filtration rate (eGFR), urea nitrogen, blood uric acid;
 - Liver function (also measured during DBTP at Week 4 and Week 8, except gamma glutamyl transferases [GGT] and lactate dehydrogenase [LDH]):
ALT, aspartate aminotransferase (AST), alkaline phosphatase (ALP), GGT, total bilirubin, and in case of total bilirubin values above the normal range, must include direct and indirect bilirubin, LDH.
- Hepatitis screen:
anti-hepatitis-C antibody (at Week -3 and Week 64/or permanent treatment discontinuation).

Technical formulas are described in [Section 2.5.1](#).

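### Former placebo patients have no scheduled liver panel for 12 weeks after their first alirocumab dose, and the pooled first-step liver summaries conceal this lighter testing

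*Protocol*

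**What the plan says.** In the double-blind period the visit lists for Weeks 4, 8 and 12 (Protocol 10.1.3.3, 10.1.3.5, 10.1.3.7) each include "Liver panel (ALT, AST, ALP, and total bilirubin". SAP 2.1.4.3 agrees: "Liver function (also measured during DBTP at Week 4 and Week 8", in addition to the Week 12 sample taken for all clinical laboratory tests.

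Placebo patients switch at Week 12. Protocol 10.1.4.1 states: "Note: All patients will be treated with alirocumab 150 mg Q4W from this time point". The same section says "Blood sample should be collected before the IMP administration", so their Week 12 panel is a pre-exposure value. Week 16 is a "Phone call visit (or IMP injection site visit" with no laboratory tests listed (10.1.4.2). Week 20 is an on-site visit with a fasting draw for "Lipids: total-C, measured and/or calculated LDL-C, HDL-C, TG, and non-HDL-C" (10.1.4.3). The liver panel returns at Week 24 (10.1.4.4). SAP 2.1.4.3 lists the open-label laboratory visits as Weeks 24, 36, 48 and 64.

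On the analysis side:

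- SAP 2.1.4 defines an alirocumab-exposed period, analysed at the first step only. "For placebo Q2W group: The time from the first dose of open-label IMP injection to the last dose of open-label IMP injection" plus 70 days is the TEAE window for former placebo patients. For the other two arms it starts at the first double-blind dose.
- SAP 3 cuts first-step safety data at the Week 24 visit.
- SAP 2.4.5 presents the exposed period for all patients together. One assessment in the TEAE period is enough to enter a PCSA denominator.
- SAP 2.4.5.3 drops by-visit laboratory tables for the exposed period unless the data call for them.
- SAP 2.1.4.1 identifies the ALT event of special interest from laboratory values.

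**The concern.** Any-time incidence and peak values depend on how often the parameter is measured. An ALT event taken from laboratory data cannot be recorded without a test. At the first step, a former placebo patient contributes one scheduled post-exposure liver result (Week 24). A patient randomized to alirocumab contributes four (Weeks 4, 8, 12 and 24). Both enter one denominator, and no planned table shows the difference. A reader of the pooled ALT, liver PCSA or peak ALT-versus-bilirubin output would assume roughly even surveillance. Protocol 11.5 links data up to 24 weeks to the Japanese application, so this is the output likely to be read.

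**Working it through.** **Plan's own figures (Protocol 11.1).** Arms are "53 in alirocumab 150 mg Q4W, 53 in alirocumab 150 mg Q2W, and 53 in placebo".

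- Dropout to Week 64: 1 − 0.70^(64/52) = 35.5%, stated as 36%.
- Patients remaining: 159 × 0.64 = 101.8, stated as 100.
- Detection at a 3% rate: 1 − 0.97^100 = 95.2%, stated as 95%.

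These reproduce, so the same hazard is used below.

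**Time to first scheduled post-dose panel.**

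- Former placebo: Day 169 − Day 85 = 84 days (78 to 90 with the ±3-day windows).
- Randomized alirocumab: Day 29 − Day 1 = 28 days (21 to 35 with the ±7-day window).
- Scheduled panels in the first 12 weeks on alirocumab: 1 against 3.

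**Patients affected.**

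- If all switch: 53/159 = 33.3% of exposed patients.
- With dropout: 1 − 0.70^(12/52) = 7.9% are lost by Week 12, leaving 53 × 0.921 = 48.8. All 106 patients randomized to alirocumab count as exposed, so the share is 48.8/(106 + 48.8) = 31.5%.

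**Capture of a transient rise.** The documents give no duration for ALT rises, so this is an assumption with a range: onset uniform over the first 12 weeks on alirocumab, duration d weeks, no event-driven testing. Tests at 4, 8 and 12 weeks capture min(1, d/4). A test at 12 weeks only captures min(1, d/12). Pooled capture weights the two by 106 and 48.8.

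| Duration | Tests at 4, 8, 12 | Test at 12 only | Pooled | Loss against equal testing |
|---|---|---|---|---|
| 4 weeks | 100% | 33% | (106 + 16.3)/154.8 = 79% | 21% |
| 8 weeks | 100% | 67% | (106 + 32.5)/154.8 = 90% | 10% |
| 12 weeks or more | 100% | 100% | 100% | nil |

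For rises shorter than 4 weeks both schedules miss some (2-week rise: 50% against 17%).

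**Effect of a Week 20 panel.** Tests at 8 and 12 weeks would capture 8/12 = 67% of 4-week rises and 100% of 8-week rises in former placebo patients. Pooled capture of 4-week rises would go from 79% to 90%.

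**Chance of seeing at least one case, if every case is captured.** The 106 randomized alirocumab patients alone give 1 − 0.97^106 = 96.0% at a true rate of 3%, against 99.1% with 155 patients. At 1% the figures are 65.5% and 78.9%.

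**The case against.** A reader might infer that early ALT rises in a third of exposed patients go unseen. The documents do not support that. A rise still present at Week 24 is measured. Early discontinuation triggers the end-of-study assessments, which include a liver panel (Protocol 10.3.4, 10.1.4.10). Cutaneous allergic events and worsening injection-site reactions call for an unscheduled one (10.6.2.1). Sites follow national labels for monitoring background therapy (8.8), and PCSAs count unscheduled values (SAP 2.4.5). Only a silent rise that resolves before Week 24 and prompts no test is lost. Appendix E, to which the protocol refers for ALT increases, was not available to check.

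A reader might also infer that early hepatic safety is left unanswered. It is not. Two arms of 53, one on the same Q4W regimen, are tested at 4, 8 and 12 weeks against concurrent placebo and reported by treatment group. Protocol 4 reports no signal for ALT increase or hepatic disorders in pooled earlier studies.

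It can further be said that the pooled table is descriptive, feeds no decision rule, and already mixes about 24 weeks of exposure with about 12. Flow chart, visit lists and SAP agree with one another, and lighter testing in an open-label extension is a coherent choice.

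All of this limits the consequence. None of it removes the pooling problem: the exposed-period summaries combine unequal ascertainment, and no planned output lets a reader see it.

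**Conclusion.** The point holds as an ascertainment and reporting problem. Former placebo patients, about a third of those exposed, have no scheduled liver panel between their first alirocumab dose and 12 weeks later. Transient, asymptomatic early rises are therefore under-ascertained in them, and the pooled first-step liver summaries understate early incidence.

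For rises of 4 weeks or more with onset in the first 12 weeks, the pooled loss lies between nil and about one fifth. This assumes uniform onset, no event-driven testing and the protocol's dropout hazard; unscheduled tests would shrink it. The direction is clear, but the size cannot be fixed without a duration that the documents do not give. The randomized double-blind comparison is not affected, and no efficacy or sample-size figure is in question.

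**What to change.** **Reporting (main change).** In SAP 2.4.5 and 2.4.5.3, present the exposed-period ALT event of special interest, liver PCSAs and peak ALT/bilirubin plot separately for former placebo patients and for patients randomized to alirocumab, with the number of liver tests per patient in each group. This costs a SAP edit and a few extra table columns. It is also in line with Protocol 11.4.3, which describes safety summaries by treatment group.

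**Measurement (optional, low cost).** The sponsor could run the liver panel on the sample already drawn at Week 20, with matching changes to flow chart 1.2, Protocol 10.1.4.3 and SAP 2.1.4.3. Under the dropout hazard 159 × 0.921 = 146 patients enter the open-label period, so this means at most about 150 extra panels, with no added visit or venepuncture. It brings the first scheduled post-dose test forward from 12 to 8 weeks and gives 2 tests against 3. Because it narrows the gap without closing it, the separate reporting is needed either way.
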